2.2 Risk/Benefit assessment

risk assessment:

This study was an observational one, and the core intervention was only a single venous blood sample collection of 3mL (approximately 1ml of serum). This operation

is a routine and mature medical practice in clinical practice, with extremely low and controllable risks.

Benefit evaluation:

Cancer patients: They will not receive immediate individualized diagnosis or treatment recommendations from this study. However, the data it contributes will drive the development of better tumor markers, which may benefit its future disease management (such as more precise follow-up monitoring).

Healthy control subjects: Contribute to establishing baseline standard values for healthy populations and promote public health. After the research is completed and the method is mature, the baseline data in which it participated may provide a reference background for its own future similar screening.

三、 Research objectives and endpoints

3.1 objective

3.1.1 main purpose

To evaluate the differences in serum histone succinylation between malignant solid tumors and healthy individuals, in order to verify its early screening value.

3.1.2 secondary objective

To clarify the correlation between histone succinylation modification in serum and different types of tumors and tumor stages, and to statistically analyze the correlation between histone succinylation in serum and therapeutic effects (including surgical treatment, radiotherapy, and systemic therapy) as well as clinicopathology.

3.2 evaluation index

The evaluation indicators are: the sensitivity, specificity, positive predictive value, negative predictive value of the serum histone succinylation screening method, and the predictive value of the Youden index (early diagnosis, therapeutic effect evaluation and prognosis).

四、 study population

4.1 inclusion criteria

case group

- 1) ≥ 18 years old, gender not limited;
- 2) Malignant solid tumors diagnosed by cytology or histology require subsequent anti-tumor treatment (systemic therapy, radical or concurrent chemoradiotherapy/radiotherapy, or surgical treatment).

control group

- 1) ≥ 18 years old, gender not limited;
- 2) Non-tumor patients undergoing health check-ups;

4.2 exclusion criteria

- 1) Pregnant women
- 2) Those with severe mental disorders or language communication disorders;
- 3) Other circumstances where the researcher deems it unsuitable to participate in this study.

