5.2 Research design process

5.2.1 Study the specific implementation process

1. Phase One: Screening and enrolling the population

- i. Conduct ethical reviews and clinical research protocol reviews for the project;
- ii. It is planned to select 500 patients with malignant solid tumors, collect their basic information and sign the "Informed Consent Form".
- iii: It is planned to select 500 healthy subjects and collect basic information.

2. Phase Two: Collect blood samples for serum histone succinylation detection

[figure not shown]
Blood samples were collected from all 500 enrolled individuals and 500 healthy subjects who met the requirements for serum histone succinylation detection.

3. Phase Three: Statistical analysis of Screening Results

- i. Western blot was used to evaluate the differences in serum histone succinylation between malignant solid tumors and healthy individuals to verify its early screening value.

ii. Statistically analyze the correlation between serum histone succinylation and tumor efficacy (including surgical treatment, radiotherapy, and systemic therapy) as well as clinicopathology. The therapeutic effect was evaluated using RECIST1.1 criteria.

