5.2.2 Research flowchart

5.2.3 Blood collection process table

grouping								
	Screening period							
healthy person	D-7—D0							
Cancer patients are receiving systemic treatment		Chemotherapy cycle						
		C1D1	C2	C3	C4	C5	C6	
	D-7—D0			D1± 3		D1±3		
Cancer patients who receive radical chemoradiotherapy/radiotherapy	D-7—D0	After the completion of radiotherapy/chemoradiotherapy		Four to six weeks after the completion of radiotherapy/chemoradiotherapy				
		D _{end} D _{end} +3		On the day of follow-up				
A tumor patient undergoing surgery	D-7—D0	postoperation	Postoperative discharge day/the day before discharge					
	D1—D3							

5.3 statistic analysis

This study adopted a mismatched case-control study (500 cases in the case group and 500 cases in the healthy control group). The sample size was determined based on the effect size of the previous pre-experiment (Cohen's $d=1.2$) and considering a 10% dropout rate. All statistical analyses were performed using R, with a test level of $\alpha=0.05$. Main analysis 1) Comparison of histone succinylation levels between groups - After Shapiro-Wilk normality and Levene homogeneity of variance tests, independent sample t-tests (conforming to normal distribution) or Mann-Whitney U tests (non-normal data) were selected. Report mean difference (MD)/median difference and 95% confidence interval (CI), Cohen's d effect size; 2) Diagnostic

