efficacy evaluation - Calculate the area under the curve (AUC) and its Bootstrap 95% CI through the ROC curve, and determine the optimal cut-off value by maximizing the Youden index. And calculate the sensitivity, specificity, positive predictive value (PPV), negative predictive value (NPV), and their exact Clopper-Pearson 95% CI. Secondary analysis: 1) Subgroup correlation - One-way analysis of variance (ANOVA) or Kruskal-Wallis test was used to compare the level differences among different tumor types (Bonferroni-adjusted post hoc test), and Cuzick's trend test was used to analyze the ordered association of TNM stages; 2) Therapeutic effect evaluation - The level changes before and after treatment were evaluated using paired t-test /Wilcoxon signed-rank test; 3) Prognostic value - The baseline succinylation level (median grouping) was included in the Cox proportional hazards model. After adjusting for age, stage, and treatment regimen, the hazard ratio (HR) and 95% confidence interval (CI) were calculated. The survival curve was plotted using the Kaplan-Meier method (Log-rank test). Multivariate analysis: A Logistic regression model was constructed (including succinylation level and covariates such as age and gender). AUC was compared by DeLong test, goodness-of-fit was evaluated by Hosmer-Lemeshow calibration curve, and clinical net benefit was analyzed by decision curve (DCA). If multi-site modifications are detected, LASSO regression is used to screen biomarker combinations. Quality control: Grubbs test /Winsorize for outliers, multiple imputation (MICE) for filling <5% of missing covariates. Sensitivity analysis: Robustness was verified by excluding stage I tumors, and the 70%-30% dataset was split for cutoff value training - validation. All multiple comparisons were controlled for the false discovery rate (FDR) using the Benjamini-Hochberg method.

六、Ethical requirements

Clinical research will comply with relevant regulations such as the Declaration of Helsinki of the World Medical Congress. The research can only be implemented after it has been approved by the ethics committee before it commences.

Before each subject is enrolled in this study, the researcher is responsible for providing the subject or their agent with a complete and comprehensive introduction

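### The prognostic Cox model uses the baseline marker only as a median split, which loses about 36% of its information if the marker is roughly normal and its effect log-linear.

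*Protocol*

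**What the plan says.** Section 5.3 of the protocol lists prognostic value as the third secondary analysis. The marker's form is given in one sentence: "The baseline succinylation level (median grouping) was included in the Cox proportional hazards model". The next sentence covers adjustment: "After adjusting for age, stage, and treatment regimen, the hazard ratio (HR) and 95% confidence interval (CI) were calculated". Display and the unadjusted test follow: "The survival curve was plotted using the Kaplan-Meier method (Log-rank test").

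The grouping is therefore the covariate from which the adjusted HR is estimated, not only a device for drawing curves. The protocol does not say whose median is meant. Controls have no prognosis to model, so it is presumably the median of the enrolled cases.

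The other analyses in section 5.3 keep the marker as a level: the case-control comparison, the ROC curve, the comparisons across tumour type and stage, the before-and-after tests, and the diagnostic model ("A Logistic regression model was constructed (including succinylation level and covariates such as age and gender").

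The patients who set the median are defined broadly in section 4.1: "Malignant solid tumors diagnosed by cytology or histology require subsequent anti-tumor treatment". Section 5.2.1 plans for 500 of them, with no quota by tumour type or stage.

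**The concern.** A median split treats patients just above and just below the cut as different, and patients at the extremes as the same as those near the middle. When risk changes steadily with the level, that discards information, and a real prognostic association is more likely to be missed.

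The result is also hard to carry elsewhere. The protocol attaches no biological or clinical meaning to the median; it is wherever the middle of the enrolled case mix falls. Another centre with more late-stage patients, or other tumour types, would have a different cut point and a different high/low contrast even if the underlying relation were identical. Section 2.1.2 wants to learn whether the marker has a future in prognosis assessment, and an HR tied to one sample's median answers that poorly.

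**Working it through.** **Inputs from the protocol.** Marker form: median groups (5.3). Test level 0.05 (5.3), taken as two-sided because sidedness is not stated. Cases: 500 planned (5.2.1). Dropout 10% (5.3), so about 500 × 0.9 = 450 cases for the simulation.

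**Inputs not in the protocol, assumed here.** Number of events, HR per SD, marker distribution, and a log-linear effect. The protocol has no figure of its own to reproduce for the prognostic analysis; its sample-size statement concerns the case-control comparison.

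**1. Information kept.** For a small effect linear in the marker X, the efficiency of the split relative to the continuous covariate is the squared correlation between X and the indicator that X exceeds its median. For a normal X this is 2/π = 0.637, a loss of 36.3%.

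**2. Other shapes, effect linear on the raw scale.**

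| Marker distribution | Kept | Lost |
|---|---|---|
| Uniform | 75% | 25% |
| Normal | 64% | 36% |
| Lognormal, log-SD 0.5 | 52% | 48% |
| Exponential | 48% | 52% |
| Lognormal, log-SD 1 | 27% | 73% |

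If the effect is linear in the log of a lognormal marker, the comparison with the log-transformed covariate returns to a 36% loss.

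**3. Power (normal marker).** Continuous: Φ(ln HR × √D − 1.96). Split: Φ(ln HR × √D × √(2/π) − 1.96), with √(2/π) = 0.798.

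- D = 150, HR 1.25 per SD: ln HR × √D = 0.2231 × 12.247 = 2.733. Continuous Φ(0.773) = 0.780. Split 2.733 × 0.798 = 2.181, Φ(0.221) = 0.587.
- D = 100, HR 1.3 per SD: 0.2624 × 10 = 2.624. Continuous Φ(0.664) = 0.747. Split 2.093, Φ(0.133) = 0.553.

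**4. Events for 80% power.** Continuous: (1.960 + 0.842)² / (ln HR)². Split: that figure divided by 2/π; Schoenfeld's formula applied to the implied high/low HR agrees to within two events.

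| HR per SD | Continuous | Median split |
|---|---|---|
| 1.2 | 237 | 371–373 |
| 1.3 | 115 | 180–181 |
| 1.5 | 48 | 75–76 |

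With the events that give the continuous marker 80% power, the split has about 61%.

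**5. Simulated Cox fits** (450 patients, normal marker, exponential survival and censoring, 4000 runs per setting). HR 1.3 per SD, about 117 events: power 80% against 59%. HR 1.2 per SD, about 236 events: 78% against 58%. The information ratio was 0.61 to 0.63, close to 2/π.

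**6. Dependence on case mix.** The true HR was held at 1.3 per unit and the marker's spread among enrolled patients was varied (2000 runs each).

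| Marker SD in sample | Continuous HR per unit | High/low HR |
|---|---|---|
| 0.7 | 1.30 | 1.35 |
| 1.0 | 1.31 | 1.53 |
| 1.5 | 1.30 | 1.84 |

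The same biology gives a high/low HR from 1.35 to 1.84 according to who enrols.

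**The case against.** **The loss is not universal.** A reader might infer that a median split loses power for any monotone association. It does not. If risk steps at the median, the split keeps everything and a linear term keeps 64%. For effects that flatten at both ends (normal marker), the split keeps 87% against 84% for a linear term when the effect follows tanh(2x), and 91% against 78% for tanh(3x). The protocol states no dose-response shape. This stands: the 36% must carry its assumptions. Equally, nothing in the protocol places a step at the median, and a spline would reveal one.

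**Robustness.** The assay is a Western blot and the plan anticipates outliers. A split is insensitive to extreme values. If the effect is linear in the log of a lognormal marker with log-SD 1, a raw-scale continuous term keeps only 58%, below the split's 64%. This stands as a reason to choose the scale with care, not as a reason to dichotomise.

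**HR per SD would not cure the case-mix problem.** The sample SD also depends on who enrols: at a true 1.30 per unit, the HR per SD is 1.20, 1.30 or 1.48 for an SD of 0.7, 1.0 or 1.5. This stands, and it is why the HR should be per fixed unit. Tumour type is also absent from the listed Cox covariates, and a continuous term alone does not remedy that.

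**Section 3.2.** A reader might take its mention of prognosis beside the Youden index ("predictive value of the Youden index (early diagnosis, therapeutic effect evaluation and prognosis") as a conflict with the median cut. That sentence lists evaluation measures and mentions neither a median split nor a Cox model, so it does not support this point.

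**Standing of the analysis.** It is secondary. A median cut fixed in advance avoids outcome-driven choice of cut point and does not inflate type I error. Both are correct and limit the weight of the point. A statistical analysis plan, not shown, might add a continuous analysis; the one the protocol states would still be the split.

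**Conclusion.** The point holds in a conditional form. The protocol fixes a median split as the only form of the marker in the prognostic Cox model. For a marker roughly normal on the analysis scale with an approximately log-linear effect, this loses about 36% of the information. Over the other shapes tried, with an effect linear on the raw scale, the loss is 25% to 73%. The illustrative drop in power is from about 78% to 59% at an assumed 150 events and HR 1.25 per SD; it is not a forecast, because the protocol gives no events, target HR or distribution. The cut point and the high/low HR depend on the enrolled mix of types and stages.

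The documents do not support reading this as an invalid test or as a threat to the primary comparison. The cost is power and interpretability in one secondary analysis, and it can be avoided at almost no expense.

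**What to change.** Reword the prognostic item in section 5.3 so that:

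- the baseline level enters the Cox model as a continuous covariate, log-transformed if skewed;
- the HR and its 95% CI are reported per fixed unit, for example per doubling, rather than per sample SD;
- linearity is checked with a restricted cubic spline;
- the median groups are kept only for the Kaplan-Meier display.

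This costs a sentence or two of analysis wording. It needs no extra patients, samples or assays, since the level is already measured.

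### The prognostic Cox model and log-rank test take no account of tumour type in a cohort open to any solid tumour, so they may partly compare cancers rather than prognosis within a cancer

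*Protocol*

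**What the plan says.** All references are to the Protocol.

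- **Who is analysed.** Section 4.1 admits cases under "Malignant solid tumors diagnosed by cytology or histology require subsequent anti-tumor treatment", the treatments being "systemic therapy, radical or concurrent chemoradiotherapy/radiotherapy, or surgical treatment". There is no restriction or quota by tumour type.
- **Prognostic model.** Section 5.3, secondary analysis 3: "The baseline succinylation level (median grouping) was included in the Cox proportional hazards model". The next sentence gives the adjustment set: "After adjusting for age, stage, and treatment regimen, the hazard ratio (HR) and 95% confidence interval (CI) were calculated". No median by type is described, so the split is taken over all cases.
- **Survival curves.** "The survival curve was plotted using the Kaplan-Meier method (Log-rank test"), with no stratification mentioned.
- **Marker by type.** Secondary analysis 1 in the same section is an ANOVA or Kruskal-Wallis analysis: "test was used to compare the level differences among different tumor types". Objective 2 in section 2.1.2 also asks whether the marker can tell tumour types apart.
- **Treatment.** Regimen is not defined as a covariate. The only categories named are those in section 4.1 and, in section 5.2.1, "tumor efficacy (including surgical treatment, radiotherapy, and systemic therapy) as well as clinicopathology".
- **Sensitivity analyses.** "Robustness was verified by excluding stage I tumors", plus a 70/30 split for the cut-off. Neither concerns type.

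**The concern.** Cancers differ in prognosis, and the protocol itself treats it as plausible that they differ in marker level. If both hold, a median split over all cases puts some cancers mostly in the high group and others mostly in the low group, and the groups then differ in survival for that reason alone. Stage does not remove this, because the same TNM stage can carry a different prognosis in different cancers.

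A marker with no prognostic value within any cancer could then appear prognostic, or a real effect could be diluted. The protocol does not allow the direction to be predicted. Prognosis is exploratory in Objective 2 but is listed among the evaluation indices in section 3.2, so a reported hazard ratio would probably be read as prognostic evidence.

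**Working it through.** **No planned figure to reproduce.** The 500 per group is justified by a case-control effect size. Section 5.3 gives no event count, target hazard ratio or power for the prognostic analysis.

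**Inputs.**
- From the protocol: 500 cases; marker split at the median; adjustment for age, stage and regimen; unstratified log-rank test.
- Tumour mix from the pilot list (section 2.1.3, Figure 3), without the two myelomas: stomach 7, lung 5, pancreas 5, colon 4, ovary 4, breast 3, liver 3, bile duct 3, cervix 2, prostate 1, oesophagus 1. That is 38 tumours of 11 types.
- Assumed: no true marker effect within any type; 200 events unless stated; within-type marker SD 1; type effects on marker and log hazard each with SD s = 0.3 or 0.5 and correlation ρ; age log-HR 0.2 per SD; four stages at 0.4 per level.

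**Hand check of the mean bias.** For a roughly normal marker split at its median, the difference in mean type log hazard between the halves is about

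2·√(2/π) · Cov / SD(marker) = 1.596 · ρs²f / √(1 + s²f),

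where f = 1 − Σp² allows for the finite number of types. Here Σp² = 164/38² = 0.114, so f = 0.886.

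- s = 0.5, ρ = 0.5: 1.596 × 0.111 / 1.105 = 0.160, HR 1.17.
- s = 0.3, ρ = 0.5: 1.596 × 0.040 / 1.039 = 0.061, HR 1.06.
- If either the marker or the hazard does not vary by type, Cov = 0 and there is no bias.

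With 200 events the standard error of the log-HR is about 2/√200 = 0.141. A bias of 0.160 is then 1.13 standard errors, and a two-sided 5% test rejects about 20% of the time. The simulated rate is higher because the realised type effects scatter around that mean.

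**Simulation.** 2,000 runs per scenario, type effects redrawn each run, exponential survival, uniform censoring, the two rarest types pooled to give ten strata. Monte Carlo error is about 0.5 points at 5% and 1 point at 25%. Entries are false-positive rates (mean HR) at ρ = 0.5 and 200 events.

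| Analysis | s = 0.3 | s = 0.5 |
|---|---|---|
| Planned Cox, regimen = three treatment groups unrelated to type | 8% (1.07) | 25% (1.17) |
| Planned Cox, systemic regimens 80% type-specific, surgery and radiotherapy one level each, one to two thirds on systemic therapy | 7-9% (1.04-1.05) | 14-19% (1.10-1.14) |
| Planned Cox, all regimens 80% type-specific | 6% (1.02) | 9% (1.06) |
| Unstratified log-rank, any reading of regimen | 7-9% | 21-23% |
| Cox stratified by type | 4-6% | 4-6% |
| Log-rank stratified by type | 5-6% | 5-6% |

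Further scenarios:
- **Marker equal across types:** 5%.
- **ρ = 0:** mean HR about 1.00, but 6-11% with three treatment groups, 6-7% with type-specific regimens and 6-10% for the unstratified log-rank test. With few types, marker and hazard effects are correlated by chance in any one cohort.
- **Events (s = 0.5, ρ = 0.5):** with three treatment groups, 10, 16, 25 and 31% at 50, 100, 200 and 300 events. With type-specific regimens, 8, 8 and 9% at 50, 100 and 200.
- **Dilution (ρ = −0.5, s = 0.5, true log-HR 0.2 per SD, three treatment groups):** Cox power 30% as planned against 53% stratified; log-rank 27% against 48%.
- **Unfavourable case:** ten equal types, marker means aligned with hazards, type explaining 10-25% of marker variance, a 3- to 6-fold hazard range. The planned Cox model gave HR 1.18-1.56 and 25-95% false positives over 200 runs each; stratified, HR 0.99-1.01 and 5-7%.

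**The case against.** Section 5.3 is a summary paragraph, and strata and coding are often left to a statistical analysis plan, which is not shown. Pooling over types is inferred from the absence of any analysis by type. Regimen may mean the drugs actually given, which often follow the cancer; the Cox model is then largely protected. Even three treatment groups, if 80% determined by type, give 21% rather than 25%, and an 11-level regimen that follows type half the time gives 18%. A material effect needs a between-type SD near 0.5, correlated effects and a fair number of events, none of which the protocol supplies. Scheduled blood collection ends early (section 5.2.3) and no follow-up length is stated, so 200 events has no source. The pilot text reports elevation over normal, not differences between types. The log-rank test is a customary unadjusted companion that also ignores age and stage. A pan-tumour marker might also be meant to predict across cancers.

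Much of this limits the size, and the figures above reflect it. It does not remove the point. The Cox covariates are given as a complete list, not as examples, and type is not among them. The document offers no reading of regimen beyond broad treatment groups, and no reading protects the log-rank test. Adjusting for stage and regimen already signals that prognosis is wanted conditional on the patient's disease. Lack of pilot evidence on differences by type is a reason to guard against them, since the protocol sets out to look for them.

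**Conclusion.** The concern holds in conditional form. If marker level and prognosis both vary by tumour type, the planned hazard ratio and log-rank test are confounded by type, in an unknown direction. On the assumptions listed, the Cox false-positive rate runs from barely above nominal (6%, SD 0.3, type-specific regimens) to 25% (SD 0.5, three treatment groups), and the log-rank rate is 21-23% at SD 0.5 whatever regimen means. Fully aligned type effects are worse; a marker equal across types gives no bias. These figures show the possible size and are not forecasts, because event count, case mix and marker levels by type are all unknown. Only an exploratory secondary analysis is affected. The change should be made because it is cheap and, without it, a non-null hazard ratio cannot be read as prognosis within a cancer.

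**What to change.** In section 5.3, secondary analysis 3, stratify the Cox baseline hazard and the log-rank test by tumour type, pooling rare types, and keep age, stage and regimen as covariates. Type as a covariate is an acceptable alternative (5-6% false positives). State how treatment regimen is coded. Using the marker as a continuous variable is no substitute: without type in the model it gave 33% false positives against 25% for the split (three treatment groups, SD 0.5).

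The change is to wording only, since tumour type is already needed for the planned comparison between types. With ten strata and three treatment groups, the standard error of the log-HR rises by about 3% if type is irrelevant, 5-6% if the marker varies by type with SD 0.3, and 9-10% with SD 0.5, much the same from 50 to 300 events. As a covariate, type costs about 2, 4 and 8% at 200 events.

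Two limits remain. Some confounding persists within the pooled rare-type stratum. With about 50 events and an 11-level regimen the Cox model is overloaded with or without strata (7-8% false positives), and the stratified log-rank test then holds slightly better (6%).

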The control group was the same as the case group.

五、 study design

5.1 overall design

This study is a single-center prospective case-control study.

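### Decision-curve net benefit is computed in a 500:500 case-control sample, so it carries a 50% case share and does not apply to the screening use the study aims at.

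*Protocol*

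**What the plan says.** Protocol Section 5.1 gives the design: "This study is a single-center prospective case-control study". Section 5.2.1 sets a quota for each group: "It is planned to select 500 patients with malignant solid tumors" and "It is planned to select 500 healthy subjects and collect basic information". Section 5.3 repeats the numbers ("500 cases in the case group and 500 cases in the healthy control group") and says that the groups are not matched.

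Under multivariate analysis, Section 5.3 builds a logistic model on succinylation level with covariates such as age and gender. It compares AUCs by the DeLong test and then says that "goodness-of-fit was evaluated by Hosmer-Lemeshow calibration curve, and clinical net benefit was analyzed by decision curve (DCA".

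Section 3.1.1 states the purpose of the group comparison: "in order to verify its early screening value".

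The protocol gives no target prevalence, intercept offset, weighting or external cohort, and no caveat on these outputs. The 70/30 split in Section 5.3 serves only the cut-off value and is drawn from the same sample.

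**The concern.** When people are sampled by outcome, the quota sets the intercept of a logistic model. The slopes are not distorted, but each predicted risk refers to a population with the sampled case share.

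A decision curve is exposed to this twice. Its thresholds are absolute risks, so they are applied to predictions on the wrong scale. Its formula also uses the case share directly, and so does the treat-all line against which the curve is read.

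At stake is how the result is read. A decision curve labelled as clinical net benefit, in a study that aims at screening, will be taken as evidence that screening with this test does more good than harm. The curve as planned cannot show that.

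**Working it through.** **Inputs.** Cases and controls: 500 and 500 (Sections 5.2.1 and 5.3). Effect size: Cohen's d = 1.2 (Section 5.3). The protocol states no prevalence and no net-benefit figure, so there is none to reproduce. Screening prevalence p is my assumption: 1%, range 0.5% to 2%. I also assume a single equal-variance binormal marker, N(0,1) in controls and N(1.2,1) in cases.

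**Case share.** 500/(500 + 500) = 50%. A logistic model with an intercept has a mean predicted risk equal to this share in its own sample.

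**Predicted risks.** To move from a 1:1 sample to prevalence p, the intercept shifts by ln[p/(1-p)]: -5.29, -4.60 and -3.89 for 0.5%, 1% and 2%. A predicted 80% has odds 4. At 1% the odds become 4 × 0.01/0.99 = 0.0404, a risk of 3.9%. At 0.5% and 2% the risk is 2.0% and 7.5%. In one simulated fit on 500 + 500, applied to a million people, the mean predicted risk was about 0.38 at each prevalence, an overprediction of about 19-fold (at 2%) to 76-fold (at 0.5%).

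**Net benefit.** At threshold t, with w = t/(1-t):

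- model: NB = p × TPR - (1-p) × FPR × w
- treat-all: NB = p - (1-p) × w
- treat-none: NB = 0

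The sample-based risk is logistic(1.2x - 0.72), so a person is positive when x ≥ [ln(w) + 0.72]/1.2.

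*Threshold 10%* (w = 1/9). The cut-off is (-2.197 + 0.72)/1.2 = -1.231, which gives TPR 0.9925 and FPR 0.8908.

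- Sample: 0.5 × 0.9925 - 0.5 × 0.8908/9 = 0.447. Treat-all: 0.5 - 0.5/9 = 0.444.
- Same uncorrected model at 1%: 0.01 × 0.9925 - 0.99 × 0.8908/9 = -0.088. Treat-all: 0.01 - 0.99/9 = -0.100.
- Corrected model at 1%: the cut-off moves to (-2.197 + 4.595 + 0.72)/1.2 = 2.598, with TPR 0.0810 and FPR 0.00469. NB = 0.01 × 0.0810 - 0.99 × 0.00469/9 = 0.0003.

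*Threshold 50%* (w = 1). The cut-off is 0.6, with TPR 0.7257 and FPR 0.2743.

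- Sample: 0.5 × 0.7257 - 0.5 × 0.2743 = 0.226. Treat-all and treat-none are both 0.
- Uncorrected model at 1%: 0.01 × 0.7257 - 0.99 × 0.2743 = -0.264.

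| Threshold | Sample: model / treat-all | Uncorrected model at 1% (2%; 0.5%) | Corrected model at 1% (2%; 0.5%) |
|---|---|---|---|
| 5% | 0.474 / 0.474 | -0.041 (-0.030; -0.046) | 0.0009 (0.0043; 0.0002) |
| 10% | 0.447 / 0.444 | -0.088 (-0.077; -0.094) | 0.0003 (0.0018; 0.00004) |
| 20% | 0.391 / 0.375 | -0.166 (-0.155; -0.172) | 0.00006 (0.0005; 0.00001) |
| 50% | 0.226 / 0 | -0.264 (-0.254; -0.269) | about 0 |

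At low thresholds nearly all of the sample's net benefit is the treat-all line: at 10% the model adds only 0.4467 - 0.4444 = 0.002. At high thresholds the sample shows a clear gain over both reference strategies, and that gain is also lost at screening prevalence.

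**Where the sign changes.** At 1% prevalence the uncorrected model gives 0.000 at a 1% threshold and -0.010 at 2%. Net harm therefore begins at thresholds of roughly the prevalence.

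**The case against.** The strongest reply has four parts.

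- **Calibration.** The protocol uses Hosmer-Lemeshow for goodness of fit, not for absolute screening risk. Only the intercept is distorted, so comparing observed and expected counts across risk groups still tests the form of the model. This stands. A reader might infer that the calibration check is worthless or that the whole model is wrong; the protocol does not support that. Odds ratios, AUC and the DeLong comparison do not depend on the sampling ratio.
- **Net harm.** A reader might infer that the planned test would harm people who are screened. The protocol does not propose to apply the model to anyone: Section 1 speaks of exploring feasibility, and Section 2.2 says that cancer patients receive no immediate individual diagnosis from the study. The negative figures show what the uncorrected risks would do if transported, and only at thresholds above roughly the prevalence.
- **Level of detail.** Threshold range and target prevalence could be set in a statistical analysis plan, which is not at hand. This lowers confidence somewhat. It does not remove the point, because the protocol itself fixes the sample, the model, the method and the label of clinical net benefit.
- **Overlap.** PPV and NPV in Section 5.3 suffer from the same sampling ratio. The cause is shared and one stated prevalence serves both, but restating PPV and NPV would leave the decision curve uncorrected.

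**Conclusion.** The point holds for absolute risk and net benefit, and for nothing else in the multivariate analysis. Followed as written, the plan yields a decision curve that is valid only where half of those tested have cancer.

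Under the assumptions used, the sample value of 0.447 at a 10% threshold becomes -0.088 uncorrected and 0.0003 corrected at 1% prevalence. The uncorrected value is negative throughout the assumed 0.5% to 2% range at thresholds of 5% and above. The exact figures rest on that assumed range, on the binormal model and on d = 1.2 from the pilot. They also assume that the marker behaves in a screening population as it does in these cases and controls.

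The decision curve lies outside the main analysis, so this is a correction that should be made rather than a threat to the primary result.

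**What to change.** In Section 5.3, before the decision curve:

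- State a sourced screening prevalence p with a range.
- Shift the model intercept by ln[p/(1-p)] - ln(analysed cases/analysed controls). The second term is zero at exactly 1:1 and matters if dropout is unequal.
- Weight cases and controls to p in the net-benefit formula.
- Show treat-all and treat-none on the same plot.

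Otherwise drop the decision curve and limit claims to discrimination.

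In either case, keep Hosmer-Lemeshow only as an in-sample check of model form, and state that absolute calibration cannot be assessed in this design. Re-weighting the same sample to an assumed prevalence gives no new evidence on it, and a calibration slope in place of Hosmer-Lemeshow would not address the intercept. Use the same p for PPV and NPV.

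The cost is a few sentences and an offset with weights in the R code; no new data are needed. The downside is that net benefit will look much less favourable and will depend on a prevalence taken from outside the study.
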